While the staff participants will complete the same intervention, the staff will receive the intervention through a different method. Staff members will receive the intervention in a small group setting. The rationale for this method, which has been shown to be effective in delivering key educational

Table 1: Virtual Reality Simulations			
Setting: Cincinnati Children's Hospital Medical Center Pediatric Primary Care Clinic			
Scenario 1	Scenario 2	Scenario 3	Scenario 4

Narrative: 11 yo female patient presents for well-child care
 
Characters: parent and female adolescent avatars
 
Source of Hesitation: none
	
Narrative: 11 yo male patient presents for well-child care
 
Characters: parent and male adolescent avatars
 
Source of Hesitation: concerns regarding necessity, young age, and promoting sex
	
Narrative: 11 yo female patient presents for well-child care
 
Characters: parent and female adolescent avatars
 
Source of Hesitation: concerns regarding necessity, young age, and promoting sex
	
Narrative: 11 yo male patient presents for well-child care
 
Characters: parent and male adolescent avatars
 
Source of Hesitation: concern regarding that vaccine is not required by school and male patients don't need it.

Key Skills: Presumptive announcement, consistent positive messaging, strong recommendation, emphasizes timing of second dose, and addressing specific concerns without medical jargon
			

components,^{59,60} is to inform the staff (nurses, medical assistants, and other patient facing staff members—who are often the first health professional to meet with patients)^{61,62} about the communication training physicians are receiving and ensure staff members are providing consistent, positive vaccination messages that align with the VICTORI objectives. After watching a 5-minute video on evidence-based practices in recommending the HPV vaccine, participants will observe [name] or another co-investigator clinician (a clinician) participate in the VR simulation while [name] or another co-investigator facilitates the experience. Staff will be able to observe the VR scene and interactions through a projector set-up. A debrief of the VR observation will occur to reinforce background knowledge, attitudes, perceptions and consistent positive messaging.

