
Data Analysis: Repeated measures generalized linear mixed-effects regression (GLMER) will be used to test whether vaccine initiation and completion rates of 9 to 17-year-old boys and girls increase in response to VICTORI. Models will include a logit link function to model the binary patient-level response of vaccine initiation (yes/no) and a random subject-specific intercept to account for patient encounters nested within physicians. Our primary outcome, determining the increase in the proportion of patients receiving HPV vaccination seen by resident and attending physicians in response to the intervention will be tested using the GLMER model including fixed-effect terms for study month (i.e., time) and period (pre-intervention vs. post-intervention). A likelihood ratio test (LRT) for period will provide a formal test of whether vaccine initiations increase in response to the intervention. Differences in the trajectory (i.e., change in slopes) of vaccine initiations between pre- and post-intervention periods will be tested by the inclusion of an interaction term for time and group. The inclusion of a random slope for time will be determined based on assessment of model fit. Polynomial terms or restricted cubic splines will be considered to model non-linear associations in vaccine initiation (i.e., capture the possible early intervention effect and subsequent decline). Additional terms as described for resident and attending physicians in phase I will be added to capture changes in the level and slope of vaccine initiation in response to training staff in phase II. Primary analyses will be conducted for

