determining whether VICTORI increases vaccine initiation. The PPCC is staffed by 80 residents and 20 attending physicians and reflects the maximum sample size for the intervention. To inform our power calculations for this proposal, we reviewed all PPCC patient visits for 11 to 17-year-old boys and girls from July 1, 2016 to June 30, 2017. HPV vaccination was initiated in 53% of visits for residents and 34% for attending physicians with greater between provider variation for residents. In addition, attending physicians saw more patients (n=9) in this age range on average per month than residents (n=2), and graphical analyses and formal regression modeling did not support material seasonal variation in initiation rates. Simulated outcomes based on these data were used to determine the minimum detectable odds ratio (OR) for vaccine initiation according to study period (i.e. pre- vs. post-intervention) as estimated from the proposed GLMER model. For resident and attending physicians combined, we assumed a total of 70 physicians having on average four patient encounters per month, a baseline probability of vaccine initiation of 43%, and a standard deviation for the subject-specific intercept of 0.55. Study power was determined to be 80% to detect an OR=1.5 based on 10k simulations. *This corresponds to a post-intervention vaccine initiation probability of 53%; or a 10% pre- to post-intervention difference.* Thus, conducting this intervention at CCHMC is expected to provide sufficient power to detect a clinically meaningful effect size for the response.

Potential Problems and Alternative Strategies: Insufficient recruitment may occur, but we do not anticipate this to be an issue as we have successfully conducted a VR intervention focused on flu vaccination with this population.²⁶ In addition, our team and expert consultants have provided extensive recommendations to recruit providers. There is the possibility of incomplete surveys; scale items with <25% missing data will be included in the analysis.⁷⁸ Multiple imputation and/or maximum likelihood estimation will be implemented should material missing values be realized for the survey responses and we will conduct a sensitivity analyses to determine the robustness of study findings to the assumptions of the imputation model.

Aim 3: Determine modifiable barriers related to HPV vaccine non-completion for future enhancement of VICTORI accordingly

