- These sample size calculations were derived from Peduzzi et al. {Peduzzi, 1996 #3012} guideline for the minimum number of cases to include for a logistic regression. The formula used for the calculation of the minimum number of participants was $N = 10 * 18 \text{ variables} / 60\%$ (the estimated proportion of patients who completed the HPV vaccine series). The formula used for the calculation of the maximum number of participants was $N = 10 * 18 \text{ variables} / 25\%$ (the estimated proportion of patients who completed the HPV vaccine within the recommended timeframe). As a note, we will also examine the proportion of patients who meet the guidelines for timely series completion (N = 400 minimum) using the following equation: $N = 10 * 18 \text{ variables} / 45\%$ (the estimated proportion of people who completed the HPV vaccine within the recommended timeframe).
- Descriptive analyses as well as data variance and distribution to characterize variables.
- Logistic regression to determine factors independently associated with completing the HPV vaccine series including: clinic location (PPC v Hopple), type of visits at first dose, resident v attending physician, provider sex, age of patient at first dose, patient sex, patient race, insurance at first dose, and social risk screener questions.

Required dose for vaccine series completion (2 doses v 3 doses) will also be included in the descriptive analyses

Training of Study Personnel

All staff will undergo training in maintaining confidentiality and have completed the required Collaborative Institutional Training Initiative (CITI) courses and research ethics classes as required by CCHMC and Cincinnati Children's Research Foundation.

Recruitment and Consent Procedure

Aim 1: Evaluate VICTORI for acceptability and feasibility

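### The primary Aim 2 period test has no visit-type term, so an abrupt change in visit mix between the pre and post windows could be read as a VICTORI effect, or hide one

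*Combined protocol and SAP*

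**What the plan says.** Under Aim 2, Data Analysis, the primary outcome is tested in a mixed-effects logistic model of patient-level initiation, with encounters nested within physicians, "including fixed-effect terms for study month (i.e., time) and period (pre-intervention vs. post-intervention"). The decision rule is: "A likelihood ratio test (LRT) for period will provide a formal test of whether vaccine initiations increase in response to the intervention". Polynomial or spline terms for time are to be considered. The patient-level effect modifiers listed are sex and age. Visit type appears in neither place, and no Aim 2 section restricts encounters by visit type.

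Visit type does appear elsewhere. Every scenario in Table 1 is a well-child visit (for example, "11 yo female patient presents for well-child care"). The Aim 3 logistic regression of series completion lists "type of visits at first dose" as a covariate.

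The plan also collects influenza, Tdap and MCV4 rates, and fits separate models to the control site to see whether background rates change.

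Under Power considerations: "we assumed a total of 70 physicians having on average four patient encounters per month", with "a baseline probability of vaccine initiation of 43%, and a standard deviation for the subject-specific intercept of 0.55". The result: "Study power was determined to be 80% to detect an OR=1.5 based on 10k simulations".

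**The concern.** The primary test is a before-after contrast at one clinic. Anything that differs between the two windows, affects initiation and is not a linear trend is attributed to period. Visit mix is a natural candidate. If vaccination is started more often at well-child visits than at other visits, a clinic that sees relatively more well-child visits after training will show a higher initiation rate even if no physician has changed behaviour. A shift the other way would hide a real effect.

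The month term removes a steady drift but not a step. The splines are optional, and their stated purpose is to follow an early intervention effect and its later decline. The control site is modelled separately, and the other vaccines have no stated role in the primary test. The conclusion about VICTORI therefore depends on visit mix staying stable, or drifting only smoothly, and the plan does not check this.

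**Working it through.** **Inputs from the protocol (Aim 2, Power considerations; Design and Measures).** 70 physicians × 4 encounters = 280 encounters per month; 6 months before and 6 after; baseline 43%; random-intercept SD 0.55; target OR 1.5.

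**Assumptions.** Two-sided 5% test (no level is stated). The two six-month windows are treated as adjacent, because the length of the implementation phase is not given in the text. The gap in initiation between well-child and other visits is taken as 0 to 40 points, with the overall rate held at 43%.

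**Step 1: reproduce the stated power.** With month and period in the model, the standard error of the period log odds ratio is 0.145.
- ln(1.5) / 0.145 = 0.4055 / 0.145 = 2.80.
- Power ≈ Φ(2.80 − 1.96) = Φ(0.84) ≈ 80%.

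The analytic value is 79.8%, and simulation of the full mixed model gives 80.3%. The stated 80% reproduces.

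**Step 2: an abrupt rise in well-child share, with no true effect.**
- Post rate = 0.43 + gap × change in share.
- Spurious OR = odds(post) / odds(0.43), where odds(0.43) = 0.43 / 0.57 = 0.754.
- False rejection = Φ(z − 1.96) + Φ(−z − 1.96), where z = ln(OR) / 0.145.

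| Rate gap | Rise in share | Post rate | Spurious OR | False rejection |
|---|---|---|---|---|
| 0 points | 10 points | 43% | 1.00 | 5% |
| 20 points | 10 points | 45% | 1.08 | 9% |
| 30 points | 10 points | 46% | 1.13 | 13% |
| 40 points | 10 points | 47% | 1.18 | 20% |
| 20 points | 20 points | 47% | 1.18 | 20% |
| 30 points | 20 points | 49% | 1.27 | 39% |
| 40 points | 20 points | 51% | 1.38 | 60% |

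A fall in share acts the other way. A 30-point gap and a 10-point fall give 40%, so OR = (0.40 / 0.60) / 0.754 = 0.88.

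**Step 3: the same rise as a steady drift.** If the share rises linearly over the 12 months, the month term takes it up and the period OR is 1.00, whatever the gap.

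**Step 4: adjust for visit type.** If visit type is all that changed, the period OR returns to 1.00. For a true OR of 1.5 within each visit type, the standard error rises from 0.145 to 0.147–0.156, and power is about 74–79% under assumed well-child shares of 50–70% and gaps of 20–40 points.

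That is not a loss against 80%, because an OR of 1.5 within each visit type is a smaller OR once visit types are pooled. For example, take a 50% well-child share with rates of 58% and 28%.
- Post rates become 67.4% and 36.8%, averaging 52.1%.
- Pooled OR = (0.521 / 0.479) / 0.754 = 1.44.
- Unadjusted power = Φ(ln 1.44 / 0.145 − 1.96) ≈ 72%, against about 76% adjusted (standard error 0.151).

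**Step 5: well-child stratum alone.** Power for OR 1.5 is about 49% at a 50% well-child share and about 63–65% at 70%, with no shift in mix.

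**The case against.** The strongest reply is that the premise is not documented. No section gives initiation by visit type or reports that visit mix changed. With no gap there is no bias, with a 20-point gap the spurious OR is only 1.08, and a linear drift is absorbed. The team also found no material seasonal variation in July 2016 to June 2017. The other-vaccine rates and the control site would help to expose a shift in mix. All of this stands, and it makes the point conditional. It does not remove it, because none of these safeguards enters the primary test, and the seasonality check covers one earlier year in ages 11 to 17 only.

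The FY17 denominator may also have been filtered already: 537 + 557 = 1,094 of the 1,450 visits (75%) were at ages 11–12. No filter by visit type is stated, and an extract with visit type would settle the question.

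Four stronger readings are tempting, but the documents do not support them.
- **Non-well visits dilute the effect.** This holds only if VICTORI works at well-child visits alone, which is nowhere stated. The outcome is defined over patients seen, the power inputs came from all visits in the age range, and the trained skills are not tied to a visit type. If the effect is equal across visits, nothing is lost in this way.
- **COVID-19 changed the clinic's visit mix.** The COVID-19 text concerns research visits and group meetings, as reasons for remote training. It says nothing about clinic mix.
- **Encounters should be restricted to in-person visits.** Nothing in the documents shows that remote visits are in the denominator.
- **Aim 3 already supplies the field.** Aim 3 records visit type at first dose, among patients who started the series after seeing a trained or participating physician. It suggests that the field can be retrieved, but it covers neither unvaccinated encounters nor the pre-training period.

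An objection that adjustment costs power does not stand (Step 4).

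**Conclusion.** The point holds as a conditional weakness of the primary test: visit type is unadjusted, and a non-linear change in mix would load onto period. Under assumed gaps of 0 to 40 points, an abrupt 10-point rise in the well-child share alone gives a spurious OR of about 1.00 to 1.18 and false rejection of 5% to about 20%. That is well short of the target OR of 1.5, but enough to mislead the test. A steady drift does no harm.

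The shares, the gaps and the size of the shift are all assumptions. The rejection rates also assume adjacent windows and a two-sided 5% level. The documents do not show that a shift occurred or that the effect is diluted.

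**What to change.** Extract visit type (well-child v other) from Epic for every Aim 2 encounter in all periods, including encounters without vaccination. Add it as a pre-specified fixed effect in the primary mixed model. Report the model without it, and the well-child stratum, as supportive only.

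The cost is one newly extracted field and a short SAP change. The period OR becomes conditional on visit type, with a slightly larger standard error (0.147–0.156 v 0.145 under the assumptions above), and the SAP should say so. The well-child stratum has only about 49–65% power at assumed shares of 50–70%, so it should not carry the conclusion. Adjustment deals with visit mix only, not with other changes between the windows.

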Physicians (n = 70) and staff (n = 40) at CCHMC PPCC will be recruited for this study to evaluate the effectiveness of VICTORI on HPV vaccine initiation and completion rates. Physicians from PPCC will receive \$50 for their efforts. Staff will receive a \$10 gift card for their efforts.

Additionally, physicians (target number = 35) from HSNHC will be recruited to serve as the control. HSNHC participants will receive the self-directed app based curriculum component of VICTORI though will not undergo the VR simulations. Participants from HSNHC will receive \$25 for their efforts.

The primary outcome is the increase in the proportion of patients receiving HPV vaccination seen by resident and attending physicians following participation in VICTORI. These data will be obtained from the EPIC electronic medical record on a monthly timeline from PPCC 6 months prior to implementing VICTORI (baseline), the months during intervention implementation, and 6 months after the intervention (post) for physicians, as well as 6 months after the intervention (post) for staff. These data will be compared with monthly HPV vaccination data from HSNHC from the start of the study until 22 months to serve as a control. Data will be blinded and entered into a REDCap database. The research materials to be obtained from participants are data collected through audio/video recordings during VICTORI and items from validated survey instruments to evaluate secondary outcomes. These secondary outcomes include physicians' behavioral capability, self-efficacy, perceived benefits, barriers, and risk, as well as attitudes, subjective norms, and strength of recommendations. We will also collect data on staffs' behavioral capability, perceived

benefits, barriers, and risk, as well as attitudes, subjective norms and ability to provide consistent positive messaging about the HPV vaccine. We will also collect data on participant characteristics. Survey data will be collected pre-intervention, immediate post-intervention, and 3 months post-intervention for physicians and pre-intervention and immediate post-intervention for staff. Data files will be kept in REDCap. Only study personnel will have access to the data.

Aim 3: Determine modifiable barriers related to HPV vaccine non-completion for future enhancement of VICTORI accordingly.

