Next, we will implement VICTORI with staff including nurses and medical assistants in groups of up to 15-20 participants (phase II; secondary outcome). These sessions may take place through a technology-based platform to allow for social distancing dependent on the COVID-19 pandemic and institutional guidelines limiting group meetings and in-person research visits. Staff will watch a 5-minute video on evidence-based practices in recommending the HPV vaccine and observe a facilitator and clinician participating in the VICTORI VR simulations, and then engage in a 5-minute debriefing. Staff will complete a brief pre and immediate post survey assessing their perceived benefits and barriers, subjective norms, and positive messaging about the HPV vaccine on paper or via REDCap. We will collect an additional six months of monthly HPV vaccination initiation and completion data, along with influenza, Tdap, and MCV4. We will collect the same vaccination data from the HSNHC over the same study period to serve as a control. The primary outcome will be the increase in the proportion of patients receiving HPV vaccination seen by resident and attending physicians following participation in VICTORI. Additional secondary outcomes, including physicians' behavioral capability, self-efficacy, perceived benefits, perceived barriers, perceived risk, attitudes, subjective norms, and strength of recommendations, as well as staffs' perceived benefits and barriers, subjective norms, and positive messaging will be assessed via validated survey instruments created by [name] and colleagues (see Appendix B and C).^{41,49,72-76} Physicians' strength of recommendation will be self-reported, which is a common method of measuring this construct.³⁰ In addition, this method (self-reported strength of recommendation) is supported as it is positively associated with vaccination rates documented through medical records.⁷⁷ Physician and staff demographics will also be collected to assess for moderation or confounding. Confidentiality of the results will be maintained. All surveys will have unique IDs with one REDCap form, separate from the surveys including their email and ID. Surveys will also be administered through the REDCap Database. Participants will receive a total of 3 emails encouraging survey completion prior to and following completion of VICTORI. Participants will receive a newsletter periodically via email to enhance retention and provide study updates (appendix). Powerpoint slides will be presented in clinic to as a retention tool as well (appendix).

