physicians (resident and attending combined) enrolled in both the pre- and post-intervention periods. *Secondary analyses* will examine the intervention effect on completion rates, for resident and attending physicians separately, and for all physicians and staff combined. GLMER models as described above will also be used to assess whether background rates of vaccine initiation and completion change over the study period in the absence of the intervention at the control site (HSNHC). Additional secondary analyses will focus on identifying potential mediators of the intervention effect on PPCC providers; whether the effect of the intervention is mediated by changes in the strength of vaccine recommendations and relevant theory-based constructs. Stratified analyses and formal testing of interactions will also be used to assess whether the effect of the intervention differs (i.e. effect modification) according to baseline provider characteristics such as age, sex, and attending vs. resident status, as well as patient characteristics (female vs. male patient, age of patient). As discussed, providers at HSNHC will be receiving the self-directed app-based curriculum component of VICTORI though will not participate in VR simulations and thus will not engage in deliberate practice of curricular skills. HSNHC providers survey responses will be compared to PPCC providers to assess for relevant changes in theory-based constructs including physicians' behavioral capability, self-efficacy, perceived benefits, barriers, and risk, as well as attitudes, subjective norms, and strength of recommendations that might occur following participation in the app-based curriculum only. Survey data will be collected before the app-based curriculum, immediately post-curriculum, and three months after the curriculum. This comparison will be conducted using a two-independent sample t-test.

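### Aim 2 promises a PPCC versus HSNHC comparison of vaccination data, but its analysis section specifies no between-site vaccination contrast

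*Combined protocol and SAP*

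**What the plan says.** **The intention to compare.** Protection of Subjects, Aim 2, describes the monthly PPCC vaccination data and continues: "These data will be compared with monthly HPV vaccination data from HSNHC from the start of the study until 22 months". Aim 2, Design and Measures, adds: "We will collect the same vaccination data from the HSNHC over the same study period to serve as a control".

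**The analysis given (Aim 2, Data Analysis).**
- The primary model is a logistic mixed model with a physician random intercept and fixed effects for study month and period. "A likelihood ratio test (LRT) for period will provide a formal test of whether vaccine initiations increase in response to the intervention".
- A change in slope between the pre and post periods "will be tested by the inclusion of an interaction term for time and group". The word *group* is not defined.
- Curvature is optional: "Polynomial terms or restricted cubic splines will be considered to model non-linear associations in vaccine initiation".
- HSNHC vaccination data go into models of the same kind, fitted to "assess whether background rates of vaccine initiation and completion change over the study period in the absence of the intervention at the control site".
- The same section discloses that "providers at HSNHC will be receiving the self-directed app-based curriculum component of VICTORI though will not participate in VR simulations". It compares the two clinics' survey responses and says of this: "This comparison will be conducted using a two-independent sample t-test".

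**Power considerations** cover only the PPCC pre-post odds ratio: 80% power for OR 1.5.

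**The concern.** HSNHC is called a control, and its vaccination data are to be compared with PPCC's, yet no stated model contains both clinics. A reader would have to set a PPCC period effect beside an HSNHC period effect and judge by eye. One effect being significant and the other not is not a test of whether they differ.

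This matters because the primary test is a within-clinic change. A linear month term absorbs steady drift. It does not absorb a step that falls near the pre/post boundary, and such a step at both clinics could be credited to VICTORI. The control data could address this, but the plan does not say how. The method would then be chosen after the data are seen.

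**Working it through.** **1. Is a between-site vaccination contrast specified anywhere?**

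| Analysis | Clinics in the model | Outcome | Tests difference in change? |
|---|---|---|---|
| Primary LRT | PPCC | Initiation | No |
| HSNHC GLMER | HSNHC | Initiation, completion | No |
| t-test | Both | Survey constructs | Not vaccination |
| Aim 3 logistic regression (clinic location term) | Both | Series completion among initiators | No pre/post term |

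The *time and group* interaction appears in a sentence about pre versus post slopes, and no site variable has been introduced. Pre/post is therefore the likelier meaning, though the wording is ambiguous.

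**2. The plan's own power.** Inputs from Power considerations: 70 physicians × 4 = 280 encounters a month, 43% baseline, random-intercept SD 0.55. Assumed: 6+6 months with no gap, two-sided 0.05. Simulating the month + period model gave 79.7% (600 runs). By approximation, power ≈ Φ(ln OR / SE − 1.96). With SE 0.146, 0.405 / 0.146 = 2.78 and Φ(0.82) ≈ 79%. The stated 80% reproduces, and it belongs to the one-clinic test. Percentages below use unrounded standard errors, so the last digit may differ slightly from hand arithmetic.

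**3. The stand-alone HSNHC model.** FY17 volume (Aim 2, Setting and Population) is 357 / 12 = 29.75 visits a month at 51%. SD 0.55 is assumed here too. For a step of OR 1.5:
- 6+6 months: SE 0.455, power about 15%. The 95% CI spans a factor of exp(1.96 × 0.455) ≈ 2.4 either way.
- 6+16 months (an assumed split of the 22 months): SE 0.296, power about 28%.

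**4. A shared step credited to VICTORI.** Assumed: no VICTORI effect and a step of OR 1.3 (ln 1.3 = 0.262) at both clinics. PPCC volume is 280 a month (the plan's figure) or 1450 / 12 = 120.8 (FY17).

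| Timing of step | 280/month: SE, share significant | 120.8/month: SE, share significant |
|---|---|---|
| Inside a dropped 3-month gap | 0.204, 25% | 0.313, 13% |
| Inside a dropped 6-month gap | 0.265, 17% | 0.405, 10% |
| No gap, exactly at the boundary | 0.146, 43–44% | 0.223, 22% |

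With no gap at 280 a month, a step one month off the boundary gives 11–12%, and two months off gives 5%. The gap lengths are assumptions.

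**5. What an added site × period contrast could detect.** 6+6 months, two-sided 0.05, ratio of odds ratios 1.5. HSNHC volume is 29.75 (FY17), 7 × 9 + 28 × 2 = 119 (PPCC per-physician rates assumed) or 35 × 4 = 140 (four per physician assumed).

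| PPCC / HSNHC per month | Parallel trends: SE, power | Site-specific slopes: SE, power |
|---|---|---|
| 120.8 / 29.75 | 0.249, 37% | 0.505, 13% |
| 280 / 29.75 | 0.234, 41% | 0.477, 14% |
| 280 / 119 | 0.132, 87% | 0.267, 33% |
| 280 / 140 | 0.125, 90% | 0.252, 36% |

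The site-slope column assumes no gap. With a 3- or 6-month gap, and ignoring the random intercept, site-slope power is 9–23% or 8–15%.

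If the app alone gave OR 1.2 and all of VICTORI OR 1.5 (both assumed), the contrast is 1.5 / 1.2 = 1.25. Power is then 15–43% with parallel trends and 7–14% with site slopes.

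FY17 counts cover ages 11–17 and the study covers 9–17, so true volumes may be higher.

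**The case against.** **The declared design is single-site pre-post.** The Aim 2 hypothesis is stated against pre-intervention rates. This stands, and it is why the PPCC test should remain primary. A reader might infer that the primary analysis is invalid or that the HSNHC data go unused. The documents support neither: HSNHC has its own model.

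**The comparison may be meant informally.** The sentence sits in a data description, and applying the same model at HSNHC naturally yields a parallel period estimate. That is a fair reading, but it still leaves the difference in change unestimated.

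**Other vaccines are tracked.** Design and Measures collects influenza, Tdap and MCV4 data at both clinics. These partly guard against a general vaccination shift. They would miss an HPV-specific one, and no model is named for them.

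**No material seasonality was found in the FY17 data.** This bears on seasonal variation, not on one-off shifts.

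**The size is easily overstated.** A reader might take 43–44% as the false-positive rate. That figure needs every physician to switch in a single month with the step exactly there, whereas the plan describes data collection over months of implementation. Nor do the documents report any background step. Their pandemic remarks concern how sessions and consent are delivered.

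**HSNHC is described as without the intervention.** A reader might call this an error, since its physicians get the app. VICTORI is defined as app plus VR and the section discloses the app, so the phrase is defensible. *App only* would be clearer.

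**Conclusion.** The gap is real and can be read directly from the text: a comparison of vaccination data is promised, and the Aim 2 analysis provides none. Separate models cannot fill it, and at FY17 volume the HSNHC model is too imprecise (15–28% power for OR 1.5) for a null result to reassure.

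The possible consequence is conditional. For an assumed shared step of OR 1.3 within a dropped implementation gap, a spurious PPCC finding would occur about 10–25% of the time, depending on gap length and volume. The no-gap aligned figure is a worst case. All these figures rest on the assumed step, on two-sided 0.05 and, for HSNHC, on an assumed random-intercept SD.

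Severity is minor to moderate. The primary test and its power stand, and the missing contrast would be a supporting estimate only.

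**What to change.** 1. Keep the PPCC likelihood ratio test as primary.
2. Add one supporting GLMER on both clinics: physician random intercept, categorical calendar month, site, and site × period, with period set by PPCC's calendar phases. Report the interaction OR and 95% CI beside each clinic's own period OR and CI. Give a site-specific-slope version as a sensitivity analysis.
3. Label the contrast app + VR (plus staff training in phase II) versus app alone. State in advance that a value near 1 is not proof of no VICTORI effect.
4. Define *group* in the slope interaction.
5. Reconcile who is recruited at HSNHC. Recruitment and Consent Procedure, Aim 2, invites attending physicians there, about 7 people according to Setting and Population. Protection of Subjects targets 35 physicians, and Setting and Population includes residents.

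**Cost.** SAP wording and one model on data already being collected; the primary test is untouched. Categorical month absorbs a step shared by both clinics whatever its timing. The limits should be stated: the contrast relies on parallel trends with one clinic per arm, cannot remove a PPCC-only shift, and cancels any app effect common to both clinics. Power is modest unless HSNHC volume is far above FY17, so it should be reported as an estimate and not used as a gate.
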